The Nephrotic Syndrome Study Network (NEPTUNE) has been created and charged with the purpose of accomplishing the specified study goals. NEPTUNE is comprised of individuals with outstanding dedication and multi-disciplinary investigative expertise. NEPTUNE came into being in large part due to the unflinching support, and significant commitment from the NephCure Kidney International, previously known as The NephCure Foundation, which is a lay research non-profit foundation devoted to understanding and improving the treatment of FSGS. NEPTUNE will operate in full with NephCure. The Halpin Foundation is also a lay research foundation that is supportive, committed and fully engaged with NEPTUNE. NEPTUNE was initially funded primarily through a 5-year grant award (U54 DK083912) from the NIDDK and ORD (\$6.25 million) with additional funding from NephCure (\$2.0 million) and the Regents of the University of Michigan (\$2.0 million). It has received a subsequent 5 year grant award (U52 DK083912-06) from the NIDDK (\$5.81 millions) and the Regents of The University of Michigan (\$4.2 million).

1.C. Specific Aims – Cohort A (Biopsy Group)

Participants presenting with Nephrotic Syndrome will be initially enrolled into two main concurrent cohort studies, namely the FSGS/MCD Cohort Study and the MN Cohort Study. The specific aims and research hypotheses of each of the main cohort studies and the combined cohort are outlined below.

1.C.1. Aims Related to FSGS and MCD

Specific Aim 1: To determine the rates and predictors of clinical remission of FSGS/MCD.

Hypothesis 1: After accounting for the types, duration, and frequency of immunomodulating therapy, the probability of remission of FSGS/MCD defined as change in urinary protein excretion and/or renal function

will be predicted by baseline demographic, clinical, genetic and histopathological characteristics at the time of presentation.

Specific Aim 2: To identify gene expression profiles from renal biopsies of participants with FSGS/MCD that can be used to classify participants into distinct molecular subgroups.

Hypothesis 2: Genome-wide molecular profiles obtained from renal biopsy tissue at the time of diagnosis of FSGS/MCD will independently predict the rate of remission of FSGS/MCD defined as change in urinary protein excretion and change in renal function.

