Specific Aim 3: To identify the transcriptional networks that are associated with individual genetic causes of FSGS/MCD; namely, mutations in *NPHS1*, *NPHS2*, *LAMB2*, *PLCE1/NPHS3* and *WT1*.

Hypothesis 3: Individual genetic causes of FSGS/MCD activate specific transcriptional pathways in renal tissue and the molecular characterization of these transcriptional pathways may serve as novel therapeutic targets with a high likelihood of more complete and sustained remission of FSGS/MCD.

1.C.2. Aims Related to MN

Specific Aim 4: To determine the rates and predictors of clinical remission of MN.

Hypothesis 4: After accounting for the types, duration, and frequency of immunomodulating therapy, the probability of remission of MN, defined as change in urinary protein excretion and/or renal function, will be predicted by baseline demographic, clinical, genetic and histopathological characteristics at the time of presentation.

Specific Aim 5: To identify gene expression profiles from renal biopsies of participants with MN that can be used to classify participants into distinct molecular subgroups.

Hypothesis 5: Genome-wide molecular profiles obtained from renal biopsy tissue at the time of diagnosis of MN will independently predict the rate of remission of MN defined as change in urinary protein excretion and/or renal function.

1.C.3. Aims Related to the Combined Histopathology Cohorts (FSGS, MCD, MN)

Specific Aim 6: To determine the effect of adjuvant (non-immunomodulating) therapy on the clinical remission of Nephrotic Syndrome.

Hypothesis 6: The use of non-immunomodulating therapy (including antihypertensives, lipid lowering, antithrombotic agents and dietary manipulation) will have an independent effect on the probability of remission of Nephrotic Syndrome defined as change in urinary protein excretion and/or renal function.

Specific Aim 7: To determine the rates of major medical complications in patients treated for Nephrotic Syndrome.

Hypothesis 7: The composite rates of major medical complications (vascular thrombosis, complications of kidney biopsy procedure, infection, and death) will vary according to the baseline characteristics and the types of treatment in patients with Nephrotic Syndrome.

Specific Aim 8: To evaluate the quality of life and its trends in participants undergoing treatment for Nephrotic Syndrome.

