Other measures, including screen failure for consented individuals determined to have exclusion criteria present post-enrollment, have been taken to compensate for over-enrolling in the OG group. The OG group will not be further followed, but samples and data obtained will remain available for comparative analyses.

3.F.3. Special Considerations for the Analysis of Molecular Biomarkers

[figure not shown]
The analysis of molecular biomarkers aims to identify promising genetic signatures used in the building of a prediction model for clinical outcomes. To screen the large number of potential predictors without losing analytical power, we would proceed in a hypothesis generating manner. Regression analysis of the clinical endpoint on biomarkers allows us to obtain P-values in the testing of their association, and a threshold value of false discovery rate would be set to determine a pool of potentially important biomarkers. These selected biomarkers will then be analyzed and grouped according to the relevance of their biological functions available in various databases. For example, biomarkers in a common transcriptional network may form a molecular signature panel. Such various panels can be further tested for the association with the clinical endpoint via the method of ridge regression. Ridge regression enables us to bypass the analytic difficulty due to highly correlated biomarkers in the model and hence obtain robust results.

3.F.4. Prediction Model Combining Molecular Biomarkers and Auxiliary Variables

The primary objective of the data analysis is to build a predictive model that uses both molecular biomarkers and auxiliary predictors to classify patients into one of two clinical states of the primary endpoint, Complete Remission/Partial Remission (CR/PR) and No Remission/Relapse (NR/R). The second endpoint is the presence or absence of the loss of renal function. In addition to 20,000 molecular markers, there are 74 auxiliary predictors collected from both cohort studies, including 38 histopathology variables, 15 laboratory variables, 15 clinical and demographic information variables, and 6 treatment variables.

Given the large number of predictors, we take a three-stage data analysis strategy consisting of variable screening, model building, and model validation. Figure 1 shows a schematic flow of steps for the model building.

Figure 1: Schematic illustration of analytic steps taken to model building.

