The first stage of analysis is a variable screening analysis, in which we perform univariate analysis. The aim of this study is to evaluate basic distributional characteristics of each predictor and pairwise correlation between the response and each predictor, as well as that between each pair of predictors. In this analysis, we also examine if transformations on some predictors are needed and if high-order predictors such as interactions and polynomial predictors are potentially useful predictors.

At the second stage of analysis, we build a predictive model for the clinical endpoint. First, we perform univariate logistic regression of the clinical endpoint on each of the predictors to detect promising predictors. To deal with the multiplicity in the test, we control a common significance level α_m on molecular markers and α_c on auxiliary predictors. At different levels of α_m and α_c , we obtain several sets of molecular and auxiliary predictors. For example, we may control α_m at 10^{-8} and α_c at 10^{-4} according to the Bonferroni's conservative type I error control. Using a set of the selected predictors, we invoke ridge logistic regression to build a predictive model, which essentially provides a linear classifier to determine the membership of a patient with a clinical class.

At the final stage of model building, we use the ROC curve method to select the final model from a small pool of candidate predictive models. To do this, we split the sample into the training set and the test

set at $(2/3n):(1/3n)$ (96-98) randomly with multiple rounds, say 100. For the sample size 200, the split is 135:65, and for the sample size of 250, the split is 170:80. At each round, we use the training set to build a predictive model and the test set to evaluate its performance of prediction by the AUC, acronym for the area under the receiver operating characteristic (ROC) curve. We use the averaged AUC to determine the final predictor model with the best averaged prediction power.

3.F.5. Sample Size and Power Considerations

3.F.5.a. Overview

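### Hypotheses 1 and 4 adjust baseline predictors of remission for total duration and frequency of therapy, which partly follow from response; if such variables reach the 3.F.4 classifier, its AUC can be inflated

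*Protocol*

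**What the plan says.** Hypothesis 1 (section 1.C.1, FSGS/MCD) states that, "After accounting for the types, duration, and frequency of immunomodulating therapy", the probability of remission "will be predicted by baseline demographic, clinical, genetic and histopathological characteristics at the time of presentation". Hypothesis 4 (section 1.C.2) repeats the condition for the other cohort: "After accounting for the types, duration, and frequency of immunomodulating therapy, the probability of remission of MN". The predictors are tied to presentation. The adjustment variables are tied to no time point.

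Section 3.F.4 builds a logistic classifier of complete or partial remission against no remission or relapse. Its 74 auxiliary predictors include "15 laboratory variables, 15 clinical and demographic information variables, and 6 treatment variables". The six treatment variables are not named or dated. Models are compared over repeated random 2/3 to 1/3 splits: "We use the averaged AUC to determine the final predictor model with the best averaged prediction power". Section 3.F.5.e adds Cox and recurrent-event analyses and does not mention time-varying therapy.

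Both kinds of treatment data will exist. Section 3.A.1 records medication changes throughout follow-up. Section 3.B.10 collects prior therapy at enrollment for children, section 3.C.2 takes medication use in the baseline history, and Appendix 8.A has a medication log at the biopsy visit.

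**The concern.** The study does not assign therapy, so how long and how often a participant is treated can depend on how the disease responds. The protocol's background describes such practice for children: section 1.C.4 has treatment first and biopsy decided on initial response, and section 2.A.3 has further agents given for relapse, steroid dependence or resistance. Total duration and frequency over follow-up are therefore partly consequences of remission or its absence.

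Two things are at stake. First, Aims 1 and 4 exist to estimate baseline associations with remission, and adjusting for a consequence of the outcome changes those estimates. Second, section 2.A.6 wants a predictor that helps decide whom to treat. Such a predictor cannot use the eventual length of the treatment being decided. A model selected on AUC will favour any variable that carries the outcome, and would lose that advantage when applied at biopsy.

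**Working it through.** The protocol gives no AUC for a model with treatment variables and no rule linking therapy to response, so there is no stated figure to reproduce. The predictor count is consistent: 38 + 15 + 15 + 6 = 74. The strength and form of the link below are assumptions, shown over a range.

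**Check 1: duration alone, therapy with no effect.**
- Inputs (assumed): exponential time to remission T, median 14 or 30 months; planned course C uniform on 4 to 24 months, independent of T; n = 200,000 per scenario.
- Outcome: remission by 36 months. Proportion remitting = 1 − 2^(−36/median): 1 − 2^(−36/14) = 0.83 and 1 − 2^(−36/30) = 0.56.
- Duration D = min(T + k, C), where k is the number of months therapy continues after remission. AUC is scored with shorter D pointing to remission.
- C carries no information on remission and therapy does nothing, so the AUC of anything about therapy knowable at biopsy is 0.50.

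| Stopping pattern | AUC, median 30 | AUC, median 14 |
|---|---|---|
| Stops at remission (k = 0) | 0.69 | 0.74 |
| Continues 6 months after remission | 0.59 | 0.61 |
| Continues 12 months after remission | about 0.53 | about 0.53 |
| Only 25% stop at remission | 0.55 | 0.56 |
| Half stop at remission, half for non-response at 6 months | 0.55 | 0.56 |
| All stop for non-response at 6 months | 0.41 | 0.37 |

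In the last row the direction reverses. A fitted model would use the reversed sign, so it still discriminates (1 − 0.41 = 0.59; 1 − 0.37 = 0.63).

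**Check 2: distortion of a baseline association.** Same set-up with k = 0, and a binary baseline factor with hazard ratio 2.
- Unadjusted odds ratio at 36 months, median 14 in the reference group: non-remission is 2^(−36/14) = 0.168 against 0.168² = 0.0283, so OR = (0.9717/0.0283) / (0.832/0.168) = about 6.9; the simulation gives 7.0.
- Adjusting for D moves it from 7.0 to 5.2. With median 30 it moves from 3.3 to 3.0.

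**Check 3: increment in a fitted classifier, using the protocol's splits.** Ridge logistic regression, five baseline predictors, 50% remission, 1,500 replicates, n = 250 split 170:80. One duration variable is γ standard deviations shorter in remitters. In the middle column one baseline predictor has log odds ratio 0.7 per SD.

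| γ | Test AUC without → with duration, baseline signal | No baseline signal |
|---|---|---|
| 0 | 0.660 → 0.657 | 0.500 → 0.501 |
| 0.25 | 0.660 → 0.669 | 0.501 → 0.538 |
| 0.5 | 0.661 → 0.702 | 0.501 → 0.611 |
| 1.0 | 0.662 → 0.789 | 0.500 → 0.743 |

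Results for n = 200 (135:65) are within about 0.01. The gain appears in the test set because the dependence is present in both parts of every split.

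If longer therapy also promotes remission (log odds ratio 0.5 per SD, baseline signal present), γ = 0.5 gives 0.651 → 0.648, so the two effects cancel; γ = 1.0 gives 0.652 → 0.704.

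In Check 3, with therapy having no effect, the baseline coefficient barely moves (0.706 against 0.708 at γ = 0.5). There, duration depends only on whether remission occurs. In Check 2 it depends on when remission occurs, and the odds ratio shifts. The distortion therefore also varies with the mechanism.

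**The case against.** The strongest case on the other side has four parts.

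- Hypotheses 1 and 4 are statements of adjusted association, while AUC appears only in the prediction and sample-size sections. No text carries the hypotheses' adjustment set into the classifier. This stands.
- The protocol says only "15 clinical and demographic information variables, and 6 treatment variables", and all six could describe therapy before or at biopsy, for which data are collected. A statistical analysis plan, not shown here, may say so. This also stands, so the AUC point can only be conditional. It does not rescue Hypotheses 1 and 4, where the protocol itself names duration and frequency as adjusters.
- Therapy is also a cause of remission, which is a sound reason to account for it. A reader might infer that the model conditions on the outcome itself. The documents do not support that: the variable is affected by both treatment choice and response, and the two influences can offset.
- Stopping every course at the moment of remission is an extreme assumption that appears nowhere in the protocol. This is correct, and is why a range is given.

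A reader might also extend the point to Hypothesis 6, which expects non-immunomodulating therapy "will have an independent effect on the probability of remission of Nephrotic Syndrome". That does not follow. The protocol fixes no exposure definition or model there, and the Cox analyses of section 3.F.5.e could take a time-varying exposure.

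**Conclusion.** The point holds for Hypotheses 1 and 4 as worded. Total duration and frequency of therapy are unknown at presentation and partly set by response, so adjusting for them in a logistic model of remission distorts the baseline associations. In the time-based scenarios the baseline odds ratio moved from 7.0 to 5.2 or from 3.3 to 3.0; under a simpler mechanism it hardly moved.

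For the classifier the conclusion is conditional. A reader might infer that its AUC is inflated, but the documents do not establish this because the six treatment variables are undefined. If any is a follow-up total, the test-set AUC can be inflated and splitting will not reveal it. With therapy assumed to have no effect, duration alone has an AUC of about 0.53 to 0.74 when it shortens with remission, against a true 0.50. The gain over baseline predictors runs from about 0.01 to 0.13 when they carry signal and 0.04 to 0.24 when they do not, for γ of 0.25 to 1.0. It may vanish if longer therapy also promotes remission. All of these sizes rest on assumed stopping patterns, because the protocol states none.

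**What to change.** - In section 3.F.4, restrict the treatment variables offered to the classifier to therapy received or chosen by baseline (biopsy), and say so.
- For Hypotheses 1 and 4, account for follow-up therapy as a time-varying covariate in the Cox models of section 3.F.5.e, or from a fixed landmark such as the month-4 visit, with remission counted only after it.
- Reword Hypotheses 1 and 4 to match.

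The cost is wording and the use of medication data already collected; no visit, sample or treatment decision changes. A landmark analysis drops participants who remit before it, and the reported AUC may be lower than with undated treatment variables.

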Hypothesis 8: The diagnosis of Nephrotic Syndrome, its treatment and clinical outcomes will have a varied measurable effect on the quality of life of participants with Nephrotic Syndrome.

Specific Aim 9: Clinical and molecular stratification of NS via a systems genetics approach. Sub-aim 1A will identify shared and specific molecular subgroups in NS using genome-wide renal tissue gene expression profiles and determine associations between baseline characteristics and clinical outcomes in these subpopulations. Sub-aim 1B will define the association between baseline characteristics, clinical outcomes, and gene expression signatures in individuals with a defined monogenic form of NS or with single copies of deleterious alleles of known NS genes.

Hypothesis 9: A: Functionally defined subgroups of NS will exhibit specific genetic, demographic, clinical, and histopathological baseline characteristics and specific adjusted hazard rates for: (a) change in urinary protein excretion (classified as remission versus no remission); and (b) change in renal function (categorical

renal function events). **B:** Patients with known disease-causing variants and those with rare variants of uncertain significance in these genes will differ in characteristics and outcomes from those participants with SRNS who do not have rare variants in these genes.

Specific Aim 10: To test association of APOL1 risk genotype with baseline characteristics, quantitative histology, and clinical outcomes in AA NS participants and to use whole kidney expression data to discover mechanisms of APOL1-associated kidney disease.

Hypothesis 10: APOL1 risk genotypes will have clinical utility as biomarkers for outcomes in AA NS participants and integrated analysis of whole genome transcriptomes and genetic variation in this population will permit discovery of the molecular mechanisms responsible for pathogenicity.

Specific Aim 11: To define non-invasive molecular predictors of outcome in functionally defined subgroups of NS. Candidate biomarkers, both discovered by NEPTUNE as published by others, will be tested in the NS cohort as biomarkers for renal outcomes and responses to therapy. Biomarker signatures will be linked to intra-renal genetic and molecular pathways.

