The majority of young children with new-onset NS have disease onset and flares that often follow an infectious or allergic event. They may have resolution, persistence or disease progression to ESKD. At onset, children with NS are routinely exposed to 8-12 weeks of corticosteroids as a diagnostic and treatment intervention [2]. The short term clinical outcomes following this approach are: 35% infrequently relapsing NS (IRNS), 40% chronic frequently relapsing/steroid dependent NS (FRNS/SDNS), and 25% steroid resistance (SRNS). Over time, an additional 20% of previously labeled IRNS or FRNS/SDNS patients will develop late SRNS[3]. There are no proven methods to predict disease course at the onset of NS. The armamentarium of non-specific therapies for FRNS/SDNS to alleviate steroid toxicity includes cyclosporine, tacrolimus, mycophenolate mofetil, cyclophosphamide, and rituximab, all of which carry significant side effects. These same medications are administered to patients with steroid resistant disease with a dismal rate of success in achieving sustained remission. Severe adverse events include peritonitis, pneumonia, septicemia, thromboembolism, diabetes, and acute kidney injury and they complicate 16% of the 5,000 NS-associated hospitalizations in US children annually [4]. Refractory NS is one of the leading causes of end stage kidney disease (ESKD) in children [5]. There is growing consensus that the steroid response-based taxonomy of NS is

inadequate because (A) it exposes children to toxic therapies despite a low likelihood of response in 25% and a poor, chronically relapsing, response in an additional 40%; (B) it does not reflect the molecular basis of the disease, (C) it inadequately predicts the heterogeneous natural history, and (D) it does not uniformly guide treatment to prevent deterioration of kidney function. The shortcomings argue persuasively for concerted and innovative investigational strategies that can be applied to the study of childhood onset NS. This effort would culminate in the development of non-invasive methods to classify participants into homogeneous cohorts with a definable course and treatment strategy. It is for this reason that the NEPTUNE investigative team, hereby submit a plan to conduct cNEPTUNE.

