Pending available funding, iron status will be assessed by serum iron and iron-binding capacity and serum ferritin concentrations. The importance of anemia and iron status has been demonstrated in both CKD progression and CVD.

3.E.5.n. Other Biochemical Measures

Electrolytes (Sodium, Potassium, Chloride, Bicarbonate), BUN, Creatinine, Glucose, AST, ALT, Total Bilirubin, Total Protein, Calcium, and CBC will be measured annually. A urine dipstick will be recorded annually for qualitative glucose, protein, and hematuria determinations. Magnesium, Phosphorous, Uric acid, and iPTH will be measured beyond baseline pending available funding.

3.E.5.o. Genotyping

Each patient enrolled in the NEPTUNE will be offered the opportunity to undergo mutational analysis by exon sequencing performed by The University of Michigan Genetics Laboratory. Mutation analysis will be obtained for the following Nephrotic Syndrome genes with recessive inheritance pattern: *NPHS1*, *NPHS2*, *LAMB2*, *PLCE1/NPHS3* and for the Nephrotic Syndrome genes with dominant inheritance pattern: *WT1* (and if indicated by family history also the extremely rare causative genes *TRPC6*, *ACTN4* and *CD2AP*). If no mutations are detected in these genes, the patient's DNA will be examined by exon capture and exon sequencing to detect mutations in so far unknown nephrosis-causing genes. If sibling cases with Nephrotic Syndrome become available in the study, they will be examined by homozygosity mapping with consecutive exon capture and exon sequencing. Genes postulated to infer risk of progression of glomerular disease (including *MYH9*) will also be considered.

3.E.5.p. Cell Line Growth and Immortalization

Pending available funding, cell immortalization of blood sample leukocytes will be pursued. Immortalized leukocytes may provide the raw material to understand the cellular and molecular mechanism of kidney disease pathways.

Schedule of Biologic Specimen Collection: Biologic specimens collected during the course of the cohort studies include blood, 24-hour urine, random spot urine, nail clippings, and renal biopsy tissue. The schedule of these collections is shown in Table 6.

Table 6. Schedule of Biologic Specimen Collection in Cohort Studies

Measure	Collection Schedule
Blood specimen	Every visit
Renal biopsy tissue	Biopsy Visit and as clinically indicated
24-hour urine specimen	Every visit
Spot urine specimen	Every visit

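### Hypothesis 9B restricts only the non-carriers to steroid-resistant disease, so its contrast mixes variant status with steroid response

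*Protocol*

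**What the plan says.** Hypothesis 9B, in Protocol 1.C.3 under Specific Aim 9, has two sides.

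- Carriers: "Patients with known disease-causing variants and those with rare variants of uncertain significance in these genes". No steroid-response condition is attached.
- Reference: the carriers "will differ in characteristics and outcomes from those participants with SRNS who do not have rare variants in these genes". Steroid resistance is a condition of membership here.

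Sub-aim 1B, which the hypothesis accompanies, looks at associations in "individuals with a defined monogenic form of NS or with single copies of deleterious alleles of known NS genes", that is, in nephrotic syndrome generally. Section 3.E.5.o makes sequencing open to all: "Each patient enrolled in the NEPTUNE will be offered the opportunity to undergo mutational analysis by exon sequencing". Carriers of any steroid response can therefore be found. 9B itself speaks only of characteristics and outcomes. Part A of the same hypothesis names the outcomes as remission versus no remission and categorical renal function events. The protocol nowhere limits the carriers to SRNS, makes the 9B contrast conditional on steroid response, or names another comparator.

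**The concern.** SRNS is a label given for failing treatment, and remission is the outcome. The protocol itself describes the link. Of SRNS, Section 2.A.3 says: "These same medications are administered to patients with steroid resistant disease with a dismal rate of success in achieving sustained remission". Section 1.A reports that half of the children with SRNS in a registry needed renal replacement within two years. The reference group is thus selected on a variable close to the outcome, and the carrier group is not.

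If a variant has no effect, its carriers resemble the whole cohort while the reference resembles the part with the poorest prognosis. A difference then appears that comes from the choice of comparator, and it favours the carriers. The class most exposed is variants of uncertain significance, because whether they matter is the open question. A neutral variant could be reported as associated with more remission or better-preserved renal function.

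**Working it through.** The protocol states no sample size, test, power or error rate for 9B, so there is no figure to reproduce. The check asks how often the written contrast rejects when variants do nothing.

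**Inputs from the protocol.** 250 participants, the FSGS/MCD target, and two-sided alpha 0.05 (1.B). SRNS share 25% (2.A.3); this describes children after initial treatment and is the only figure given.

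**Assumed inputs.** Carrier share 10% or 20%. SRNS share also 50%, since a biopsy cohort may be enriched. Remission 30% or 40% in SRNS, and 80% or 90% otherwise. Outcome binary, compared by Fisher's exact test.

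**Model with no variant effect.** Let s be the SRNS share, r_S remission in SRNS and r_N remission otherwise.

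- Carriers remit at (1 − s) × r_N + s × r_S.
- The reference remits at r_S.
- Example with 10% carriers, s = 25%, r_N = 80%, r_S = 30%: 25 carriers remit at 0.75 × 0.80 + 0.25 × 0.30 = 67.5%. The 225 × 0.25 ≈ 56 SRNS non-carriers remit at 30%. The gap is 37.5 points with no variant effect.

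**False-rejection rate, exact enumeration over both binomials.** Columns give remission in non-SRNS / SRNS.

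| Carriers, SRNS share (n carriers vs n reference) | 90/30 | 90/40 | 80/30 | 80/40 |
|---|---|---|---|---|
| 10%, 25% (25 vs 56) | 96.1% | 86.3% | 86.0% | 64.6% |
| 10%, 50% (25 vs 112) | 76.6% | 60.8% | 60.4% | 42.2% |
| 20%, 25% (50 vs 50) | 99.5% | 96.4% | 96.0% | 82.9% |
| 20%, 50% (50 vs 100) | 92.7% | 79.2% | 81.5% | 58.1% |

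In every cell fewer than 1 in 10,000 studies reject in favour of the non-carriers.

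**Is one-sided selection the cause?** Two checks say yes. With remission set equal (50/50) in SRNS and non-SRNS, the written contrast rejects at about 5% (pooled z-test). With like compared with like, using Fisher's test and the 90/30 and 80/40 columns, all carriers versus all non-carriers and SRNS carriers versus SRNS non-carriers both reject in about 4% or fewer.

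**If carriers are enriched for SRNS.** Take 25 carriers vs 56 reference and remission 80/30, with no variant effect on remission given steroid response.

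| SRNS share among carriers | Carrier remission | Fisher | Pooled z |
|---|---|---|---|
| 25% | 67.5% | 86.0% | 89.9% |
| 50% | 55.0% | 52.1% | 58.1% |
| 75% | 42.5% | 17.0% | 20.3% |
| 90% | 35.0% | 6.1% | 7.7% |
| 100% | 30.0% | 3.8% | 4.9% |

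**Wider assumptions.** With carriers 5%-20%, SRNS 25%-60%, remission pairs 90/20, 80/30 and 70/40, and 250 or 600 participants, the pooled z-test rejects in 13.9% to 100%.

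**The case against.** The best defence is that 9B means genetic versus non-genetic SRNS. Sections 1.A and 2.A.5 introduce these genes as causes of SRNS, and 2.A.5 holds that a mutation in one of them is enough to produce it. If all carriers have SRNS, the error is nominal. This stands for known disease-causing variants, where a null with carriers at average SRNS risk goes against the protocol's own premise. It does not cover variants of uncertain significance, and the sentence does not state the restriction.

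A second defence is that analysis sets and covariates for a secondary aim belong in an analysis plan, and that the protocol foresees adjusted hazard rates (Hypothesis 9A) and Cox regression with clinical covariates (3.F.5.e). It is true that no crude Fisher test is prescribed. But the comparator is stated, not left open. Adjusting for steroid response would not rescue it: carriers without SRNS have no counterpart among non-carriers who all have SRNS.

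Third, the size rests on assumptions. The 25% belongs to the Cohort B rationale, while Hypothesis 9 concerns Cohort A. Biopsy guided by initial response (1.C.4) and prior therapy (3.B.10) may enrich Cohort A children for SRNS. That shrinks the bias without removing it, as the 50% rows show.

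**Conclusion.** The point holds as a flaw in the stated comparator. As written, 9B sets carriers of any steroid response against non-carriers who all have SRNS, and so cannot separate variant status from steroid response. Under the assumptions above the false-rejection rate is about 42%-99.5%, practically always in the carriers' favour. In the 80/30 setting with 25 carriers and 56 reference participants it is about 17% if 75% of carriers have SRNS, and nominal if all do. The direction follows from the text; the size depends on carrier share and remission rates that the protocol does not give.

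A reader might infer more than the documents support:

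- That the test is bound to reject when variants do nothing. It rejects too often, by an amount that depends on how many carriers have SRNS.
- That single-copy deleterious alleles are caught in the same way. They are named in Sub-aim 1B, which has no SRNS comparator, and not in 9B.
- That truly harmful variants would be hidden. If a variant acts only by causing SRNS and nearly all its carriers have SRNS, a near-null result is the right answer to whether genetic SRNS differs from other SRNS. It misleads only if read as answering whether carriers differ from all non-carriers.
- That the study's main result is at risk. This is half of one of twelve Cohort A hypotheses, and the primary objective is the prediction model (3.F.4, 3.F.5.a).

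Severity is moderate.

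**What to change.** Reword Hypothesis 9B so that the same steroid-response restriction applies to both sides, and state which question each comparison answers:

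- SRNS carriers versus SRNS non-carriers: does genetic SRNS differ from other SRNS? Count outcomes from the point at which SRNS is established, since 2.A.3 notes that resistance can appear late.
- All sequenced carriers versus all sequenced non-carriers in the same histologic cohort: do variants relate to outcome overall, including through steroid resistance?

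Either is sound, and both may be kept. Report known disease-causing variants separately from variants of uncertain significance, because the premise that carriers have SRNS applies only to the former.

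The cost is a sentence or two of protocol text. Sequencing is already offered to every enrolled participant, so no new data are needed. The within-SRNS comparison will be small: with 250 participants, 10% carriers and a 25% SRNS share it would hold about 250 × 0.10 × 0.25 ≈ 6 carriers, and should be presented as an estimate with its interval.
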